6. STATISTICAL METHODS

The primary objective of this study is to evaluate the safety and feasibility of tvCVS delivered using the TNMTM Device (Generation 4.0) as an adjuvant treatment for patients diagnosed with mild to moderate PDD.

6.1. ANALYSIS POPULATIONS

Intent-to-treat Population (ITT): All participants who start at least one treatment with the study device will be included in this primary analysis of efficacy and safety.

Per-protocol Population (PP): All eligible participants who (1) demonstrate at least 70% adherence of the randomized expected treatments with the Study Device and (2) have completed the regularly scheduled end of treatment visit (day 84), and (3) have not had changes to medications used to treat motor and/or non-motor symptoms of PD during the trial will be included in the PP population.

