6.3 Concomitant Therapy

6.3.1 Approved Concomitant Medications

- The use of the FDA-approved pharmaceutical medications to treat the cognitive symptoms including cholinesterase inhibitors, glutamate N-methyl-D-aspartate (NMDA) receptor regulators and combination therapies will be permitted during the study so long

as the type or dose does not change during the study or the 4 weeks immediately preceding the study screening visit.

- The use of the following medications used to treat motor and non-motor symptoms associated with PD will be permitted during the study so long as the type or dose does not change during the course of the study or the 4 weeks immediately preceding the study screening visit: oral levodopa-based therapies, transdermal DRTs (e.g., rotigotine transdermal system), dopamine receptor agonists, MAO-B inhibitors and COMT inhibitors.
- The use of selective serotonin reuptake inhibitors or other anti-depression/anti-anxiety medications not specifically excluded in the Excluded Medications list will also be permitted during the study so long as the type or dose does not change during the study or the 12 weeks immediately preceding the study screening visit.
- The use of orexin receptor antagonists for the treatment of insomnia will be permitted during the study so long as the type or dose does not change during the study or the 4 weeks immediately preceding the study screening visit.
- The use of pimavanserin and quetiapine QHS at doses that do not produce cognitive deficits or daytime sleepiness will be permitted during the study so long as the medication has been taken for > 180 days and the type or dose does not change during the study or the 4 weeks immediately preceding the study screening visit.
- Medications prescribed for other concomitant illnesses are allowed so long as they are not listed in the Excluded Medications list.
- Vaccines, supplements, and over the counter medications, including those taken occasionally (for example: seasonal allergy medications), should be documented if a dose occurred during the protocol timeframe.
- When medications are prescribed for indications other than symptoms associated with PD or cognition, physicians will be encouraged to utilize the one that is least likely to impact symptoms assessed in the trial. In particular, the central anticholinergic properties of medications should be considered.

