- Changes to medications for symptoms associated with cognition are not permitted during the trial. Participants will be advised that during the trial, they should maintain patterns of usage of approved therapeutic medications that they normally use and that they should not initiate new medication (type, dosage or route of administration), medicating patterns or other interventions unless their provider deems the change to be medically necessary, as changes in concomitant treatments will interfere with the ability to attribute clinical change during the study to use of the Device. Any medically necessary changes will be recorded as concomitant medications and participants will continue in the study. Reasons for changes in medications used to treat cognitive symptoms will be recorded and participants who make changes to these medications or add new medications likely to modulate symptoms associated with cognition during the study will be included in the ITT analysis but excluded from the PP analysis.

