6.3.2 Excluded concomitant medications, drugs and supplements

- Off-state rescue medications (e.g., apomorphine injections or levodopa-based inhalers) are not permitted on days of study center visits but may be used at other times. Protocol deviations will not be accepted, and the visit should be rescheduled in circumstances

where off-state rescues were taken on the day of a visit. Off-state rescue medications may otherwise be used throughout the trial period.

- Antipsychotic Medications not specifically listed in the Approved Concomitant Medications (i.e., either neuroleptics or atypical antipsychotics).
- Medications producing side effects of cognitive deficits, delirium, psychosis, motor impairments or daytime sleepiness. For example, benzodiazepines such as clonazepam may produce cognitive deficits, however, these may be avoided at low dosages (i.e., \leq 1mg) and/or with QHS administration and therefore would be permitted under these conditions.
- Mucuna pruriens supplements
- Anti-emetics (e.g., 5-HT₃ receptor antagonists, D₂ receptor antagonists, first-generation H₁ Receptor antagonists, muscarinic antagonists, synthetic cannabinoids or SP/NK₁ receptors antagonists with anti-emetic properties) as well as corticosteroids with significant anti-emetic properties prescribed chronically (taken more than 2 times per week, consistently)
- Inhaled or ingested cannabinoids (e.g., marijuana, tetrahydrocannabinol, nabilone or cannabidiol) within 4 weeks of screening and during the study period.
- Any drug that has not been legalized on a United States Federal level
- Controlled substances that have not been prescribed under the care of a licensed professional.
- Anticholinergics with definite central activity (acbcalc.com)
- Antibody therapies used to treat cognitive decline in Alzheimer's disease (e.g., those that target amyloid).

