1. INTRODUCTION

This document describes the statistical analysis plan (SAP) for SNS-PD-004, the multicenter single arm safety and feasibility trial described in the protocol Simple, Home-use neurostimulAtion tReatment for Parkinson's disease dEmeNtia (Brief title: SHARPEN). This analysis plan is meant to supplement the study protocol. Any deviations from this analysis plan will be described in the clinical study report.

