6.4.3. Pre-study and Concomitant Medications

The number and percentage of each treatment cohort on concomitant therapies at randomization will be reported categorically including the following:

- o adenosine A2A antagonists
- o amantadine
- o anticonvulsants
- o anti-depressant/antianxiety medications
- \circ antiemetics
- \circ antihistamines
- o antihypertensives
- o antipsychotics
- central anticholinergics
- cognitive enhancers
- COMT Inhibitors
- contraceptives
- o corticosteroids
- o dystonia treatments
- o incontinence treatments
- inhaled levodopa
- o inhaled or ingested cannabinoids
- laxatives/stool softeners
- MAO-B inhibitors
- o narcotics
- o oral or transdermal dopamine agonists
- o oral levodopa-based therapies
- o oral levodopa-based therapies/COMT inhibitors
- o orthostatic hypotension treatments
- o pain/cramping treatments
- pump therapies
- o sexual dysfunction treatments
- o sialorrhea treatments
- o sleep aids
- o stimulants

Changes in medications to treat symptoms associated with PD during the trial are a protocol deviation. Changes in these medications would exclude participants from the PP analysis. Changes in medications in the ITT cohorts will be summarized descriptively.

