6.5. ENDPOINT ANALYSIS

All efficacy analyses will assume non-normality given the small sample size of the study. Paired comparisons (i.e., pre- and post-treatment measurements) will utilize Wilcoxon signed-rank tests unless otherwise noted.

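### A participant who starts a cognition-affecting drug for a non-PD illness is out of the per-protocol set under Protocol 6.3.1 but in it under SAP 6.1 as written

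*SAP*

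**What the plan says.** **Protocol 6.3.1** names two medication events that keep a participant in ITT but remove them from PP. One is a change to drugs used for cognitive symptoms. The other applies to participants who "add new medications likely to modulate symptoms associated with cognition during the study will be included in the ITT analysis but excluded from the PP" set. The same paragraph keeps participants with medically necessary changes in the study, so they can still reach Day 84.

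**Drugs for other illnesses.** Protocol 6.3.1 also states: "Medications prescribed for other concomitant illnesses are allowed so long as they are not listed in the Excluded Medications list". It adds guidance that begins "When medications are prescribed for indications other than symptoms associated with PD or cognition", but this only encourages the physician to pick the option least likely to affect the symptoms under study. The excluded list in Protocol 6.3.2 includes "Medications producing side effects of cognitive deficits, delirium, psychosis, motor impairments or daytime sleepiness".

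**SAP 6.1** lists three conditions for PP: at least 70% adherence, a completed Day 84 visit, and that participants "have not had changes to medications used to treat motor and/or non-motor symptoms of PD during the trial". All eligible participants who meet the three are to be included. SAP 6.4.3 refers to drugs for PD symptoms and says: "Changes in these medications would exclude participants from the PP analysis".

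**How the two relate.** SAP 1 says: "This analysis plan is meant to supplement the study protocol". Neither document says which PP wording governs where they differ.

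**The concern.** The Protocol's second trigger concerns what a new drug is likely to do to cognition. The SAP's only medication condition concerns what a drug is used to treat. A drug started for a non-PD illness can meet the first and escape the second.

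The lost exclusion is the one closest to the secondary endpoint, the change in MoCA. The trial has no control arm, so a cognitive change caused by a new drug cannot be separated from one caused by the device. The sponsor recognises this risk: Protocol 6.3.1 warns that treatment changes obscure attribution to the device, and Protocol 5.3 gives confounding by medication changes as the reason for stopping at 12 weeks. The Protocol synopsis commits to analysing both ITT and PP data, so someone will have to decide who is in PP. In an open-label study, that decision should not be left until scores are known.

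**Working it through.** The plan states no figure to reproduce here. The check applies both rules to the same participants.

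**Step 1. Classify by type of medication event.** Assume at least 70% adherence and a completed Day 84 visit throughout, so that only the medication rule matters.

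| Event during the trial | Protocol 6.3.1 | SAP 6.1 (3) and 6.4.3 |
|---|---|---|
| Change to a drug for cognitive symptoms | Out of PP | Out of PP, since cognitive symptoms in PDD are non-motor PD symptoms |
| Change to a drug for motor PD symptoms only | Dose and type must stay stable, but no PP consequence stated | Out of PP |
| New drug for a non-PD illness, likely to affect cognition, not on the excluded list | Out of PP | In PP |
| New drug for a non-PD illness, likely to affect cognition, on the excluded list | Out of PP | No PP consequence stated |
| New drug for a non-PD illness, no likely effect on cognition | In PP | In PP |

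The SAP is broader than the Protocol in row 2 and narrower in row 3. In row 4 it is narrower unless the word *eligible* in SAP 6.1 is read as also covering drugs started after entry. The point rests on rows 3 and 4.

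**Step 2. Can row 3 occur?** Yes. Drugs for other illnesses are allowed if not listed, the advice on choosing among them is encouragement only, and a participant with a medically necessary change stays in the study.

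**Step 3. Weight of one participant.** Inputs: 12 treated participants (Protocol 10.1, SAP 4) and the 75% completion criterion in the same sections.

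- Completers at the criterion: 0.75 × 12 = 9.
- Share of a PP set of 12: 1/12 = 8.3%.
- Share of a PP set of 9: 1/9 = 11.1%.

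The set could fall below 9 once the adherence and medication conditions are applied, and the share would then be larger.

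**Step 4. What cannot be computed.** The documents give no SD or decision threshold for the MoCA and no expected rate of new drug starts. No effect in MoCA points follows from them.

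**The case against.** **The SAP supplements the Protocol, so both rules apply together.** On that reading the participant is out of PP and nothing conflicts. This has some force: a reader might infer a flat contradiction, and the documents do not go that far. But SAP 6.1 is written as a complete admission rule, and an analyst working from it would include the participant. What stands is that the relation between the two rules is unclear. The same caution applies in the other direction. It would be uneven to call the SAP's exclusion for motor-drug changes a harmless addition while calling its silence on cognition-affecting drugs a conflict. Both are differences between the two definitions.

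**The Protocol does not say that indication is irrelevant.** That is correct. The clause sits in a paragraph about drugs for cognition, and if it meant only drugs added to treat cognition, SAP 6.1 (3) would already cover it. The effect-based reading is still the better one, because the sentence deals separately with drugs used for cognitive symptoms and then adds new drugs by their likely effect.

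**The excluded list and the word *eligible* close the gap.** They narrow it. Many drugs that impair cognition are barred, and use of a barred drug is exclusion criterion 10. But eligibility is reviewed at screening and baseline, the SAP does not define *eligible*, a drug can affect cognition without being listed, and neither document states a PP consequence for starting a listed drug as such. Such a start would at least be visible among the protocol deviations summarised under SAP 6.3.

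**The stakes are low.** Largely so. The 8.3% and 11.1% shares hold for any one participant in a set of 12 or 9 and do not measure this mismatch.

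**Conclusion.** The point holds in a limited form. As written, SAP 6.1 can keep in PP a participant whom Protocol 6.3.1 removes, and nothing in either document clearly resolves the difference. This rests on reading the Protocol trigger by drug effect, and on the participant meeting the adherence and Day 84 conditions. Each such participant is 8.3% of a PP set of 12 or 11.1% of a set of 9. How often this would happen is unknown, and the case is probably uncommon given the excluded list.

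A reader might infer that the main results are at risk. They are not: SAP 6.1 makes ITT the primary analysis set, and the go/no-go criteria (no serious adverse device effects, at least 75% completing) do not use PP membership. A reader might also infer that the PP MoCA result would be biased towards benefit. The documents give no direction, since a new drug could move cognition either way.

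**What to change.** Add to SAP 6.1 (3): *and have not added any new medication likely to modulate cognition, whatever its indication, during the trial*. State that this is judged from the concomitant-medication list without sight of outcome scores. Have the PP sentence in SAP 6.4.3 refer to 6.1 (3) instead of restating the rule.

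The Protocol text can stand: with the clause added, the SAP applies both of the Protocol's medication exclusions and keeps its own wider rule for PD drugs. A listing of MDS-UPDRS changes among participants excluded for PD-drug changes would answer a different question and is not needed here.

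The cost is one clause and one cross-reference. No new data are needed, because the Schedule of Events already has concomitant medications reviewed at baseline and at every later visit and call. The downside is that the PP set may be slightly smaller. Some judgement remains in deciding which drugs are likely to affect cognition, which is why it should be made without the scores.

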6.2. DEFINITIONS

Study day: The study day will be calculated in reference to the date of the baseline visit (Day 0).

No data collected at the study screen will be utilized in the evaluation of study outcomes.

6.3. ANALYSIS OF STUDY CONDUCT

The number of participants screened and the number of those randomized falling into the ITT and PP cohorts will be summarized.

Study treatment administration, duration of follow-up, discontinuation from study treatment and the reasons for discontinuation will be summarized by treatment group for all randomized participants. Coded protocol deviations and protocol violations will also be summarized as either Major/Important, Minor or No Impact, where:

- Major/Important are protocol deviations that might significantly impact completeness, accuracy, and/or reliability of study data OR could significantly affect a participant's rights, safety or well-being
- $\circ~$ Minor are protocol deviations with minor impact on data quality or patient safety
- No impact are protocol deviations that do not impact data quality or patient safety

6.4. ANALYSIS OF TREATMENT GROUP

6.4.1. Demographics and Baseline Characteristics

The following characteristics will be summarized for participants in each cohort (i.e., ITT and PP): age, sex, years since PD diagnosis, levodopa equivalent daily dose, race and ethnicity. Sex, race and ethnicity will be described with frequency and percentages. Age, years since PD diagnosis and levodopa equivalent daily dose will be described with minimum, 1Q, median, 3Q, and maximum values.

6.4.2. Disease characteristics

Baseline Hoehn & Yahr scores will be summarized. Additionally, motor phenotypes (i.e., tremor-dominant, postural instability gait difficulty and intermediate) classified based on the Baseline visit MDS-UPDRS part II and part III scores and previously-established methodology(Stebbins, Goetz et al. 2013). Specifically, a Tremor score will be calculated by summing all items from 2.10, 3.15, 3.16, 3.17 and 3.18 from the MDS-UPDRS. A postural instability and gait difficulty (PIGD) score will be calculated by summing all items from 2.12, 2.13, 3.10, 3.11 and 3.12 from the MDS-UPDRS. Ratios of Tremor score/PIGD score will be used to classify motor phenotypes. Ratios $\geq 1.15 =$ Tremor dominant. Ratios $\leq 0.90 =$ PIGD dominant. Scores > 0.9 and < 1.15 = intermediate. If data required to calculate the scores is missing from the Baseline 2 visit, data from the Baseline 1 visit will be analyzed. Post randomization data will not be considered. Classification will only be

performed on complete case data. Disease characteristics will be described with minimum, 1Q, median, 3Q, and maximum values.

6.4.3. Pre-study and Concomitant Medications

The number and percentage of each treatment cohort on concomitant therapies at randomization will be reported categorically including the following:

- o adenosine A2A antagonists
- o amantadine
- o anticonvulsants
- o anti-depressant/antianxiety medications
- \circ antiemetics
- \circ antihistamines
- o antihypertensives
- o antipsychotics
- central anticholinergics
- cognitive enhancers
- COMT Inhibitors
- contraceptives
- o corticosteroids
- o dystonia treatments
- o incontinence treatments
- inhaled levodopa
- o inhaled or ingested cannabinoids
- laxatives/stool softeners
- MAO-B inhibitors
- o narcotics
- o oral or transdermal dopamine agonists
- o oral levodopa-based therapies
- o oral levodopa-based therapies/COMT inhibitors
- o orthostatic hypotension treatments
- o pain/cramping treatments
- pump therapies
- o sexual dysfunction treatments
- o sialorrhea treatments
- o sleep aids
- o stimulants

Changes in medications to treat symptoms associated with PD during the trial are a protocol deviation. Changes in these medications would exclude participants from the PP analysis. Changes in medications in the ITT cohorts will be summarized descriptively.

6.5. ENDPOINT ANALYSIS

All efficacy analyses will assume non-normality given the small sample size of the study. Paired comparisons (i.e., pre- and post-treatment measurements) will utilize Wilcoxon signed-rank tests unless otherwise noted.

6.6.1 PRIMARY ENDPOINTS

(Safety) MDS-UPDRS Parts I, II & III summed score: Changes will be considered to be clinically meaningful worsening if the median difference meets or exceeds the previously established MCID (+5.2 points for clinical worsening) (Makkos, Kovacs et al. 2018). Two-sided, 90% confidence intervals for the combined MDS-UPDRS Parts I, II, and III scores at baseline and the end of treatment period will be constructed. If the median difference (baseline- end of treatment) is less than 5.2 and the confidence interval of the difference (baseline – end of treatment) contains 5.2, then the no clinically meaningful worsening.

(Feasibility)

- **Retention rate** will be defined by the percentage of participants that complete assessments required for analysis of the secondary endpoint:
 - High retention: >90%
 - Moderate retention: 60-90 %
 - Low retention: < 60 %
- **Treatment adherence** rate for each participant will be defined as the percentage of twice-daily treatments with the neuromodulation device completed during the 12-week treatment period:
 - High adherence: >84%
 - Moderate adherence: 55-84 %
 - Low adherence: < 55 %
 - Treatment adherence is captured by the study device and will be reported summarized with minimum, 1Q, median, 3Q, and maximum values. Treatment adherence of \geq 70% is required for inclusion in the Per Protocol cohort.

Adverse Events (AEs): Participants will be assessed for AEs every two weeks at minimum (either at study visits or during phone calls). For each group, the AEs will be summarized with frequency and percentage by preferred (PT) term, with all participants in that treatment group as the denominator. Classification will utilize MedDRA System Organ

Class (SOC) based on MedDRA® Version 26.0 or other terminology/classification common to Parkinson's disease (e.g., falls, freezing of gait, etc.). AE incidence will be summarized by both severity and causal relationship to Device treatment (as determined by the blinded Principal Investigator or designated study personnel). AEs deemed to be of "possible" or "probable" relationship or "related" to the Device will also be considered as device related. Additionally, the number of events and number of device-related events per person will be reported as a distribution.

The AE summary tables will provide an overall summary of AEs including the number and percentage of participants who experienced any AE, any SAE, any ADE, any SADE, any UADE, and any discontinuations in study participation due to an AE.

